# Weighting, Nonresponse Bias Analysis, Missing Data Compensation, and Variance Estimation

## 6

### 6.1 Overview

We plan to use standard design-based methods for weighting and variance estimation that will lead to confidence intervals on means and percentages, and hypothesis tests on contrasts of means and percentages. Base weights will be computed as the reciprocals of the probabilities of selection. We expect there will be missing data given the large number of planned interviews for each sampled member and the high likelihood that some individuals will miss some interviews. If analyses were restricted to only complete cases, information from the incomplete cases would be lost and the analyses would ignore the possibility that there are systematic differences between the complete cases and incomplete cases. We will address this potential nonresponse bias by a combination of nonresponse adjustments to the sampling weights and imputation of missing data.

Weighting adjustments can be used to reduce nonresponse bias. However, unless a separate set of weights is developed for each subsample being analyzed, weighting adjustments tend not to deliver much lower variance than the simple procedure of analyzing only complete cases. In fact, weighting adjustments tend to increase variances beyond what one sees in the simple procedure of only analyzing complete cases. Although weights are not as transparent as restricting the analysis to include only complete cases, they are still fairly easy to understand and are well accepted in the survey tradition, at least for cross-sectional surveys or cross-sectional analyses of longitudinal surveys.

Imputation is another tool we will use to address missing data and the associated nonresponse bias. Imputation has the important advantage that analyses based on imputed datasets can be exceptionally clear to a wide set of audiences. However, when imputation is done it is important to document clearly which data on microdata sets are imputed, and to explain the uses for which the imputed data are more or less well suited.

We begin our discussion with our approach to base weights (Section 6.2). This will be followed by a section on our plan for weighting and imputation (Section 6.3). Finally, we close with sections on nonresponse bias analysis (Section 6.4) and variance estimation (Section 6.5).

## 6.2 Base weights

We will develop sampling weights aimed at yielding nearly unbiased estimates of population parameters such as the breastfeeding initiation rate. These weights will be based on Horvitz-Thompson weights, equal to the inverse of the probability of selection. Layered over these will be adjustments for nonresponse across the interviews (called “waves” for weighting purposes) of the study. One set of weights will be developed for analyses of the core sample by itself. A different set of weights will be developed for joint analyses of the core and supplemental sample samples.

### Core Sample

The Horvitz-Thompson core-sample weight for an infant will be

$$W_{Bijk} = \frac{52}{22} \frac{M_i}{4M_{ij}} \frac{E_i}{2} \frac{C_{ij}}{D_{ij}} \frac{22L_{ij}}{L_{ij}} \frac{N_{ij}}{n_{ij}},$$

where the first factor adjusts for the fact that the field period contains only 22 of the 52 weeks in a year,,  $M_i$  is the count of new enrollments in the  $i$ -th stratum according to the PC2010,  $M_{ij}$  is the count of new enrollments (defined the same way from the same source) in the  $j$ -th first-stage sampling unit in  $i$ -th stratum, the 4 in the denominator adjusts for the fact of sampling four first-stage sampling units per stratum in the first phase of selection,  $E_{ij}$  is the number of eligible first-stage units among the 4 sampled in the  $i$ -th stratum, the 2 in the denominator accounts for the fact that 2 first-stage units will be selected in the second phase among the  $E_i$  eligible,  $C_{ij}$  is the count of clients in same first-stage sampling unit according to local reports at the time of first-stage sampling unit scouting,  $D_{ij}$  is the count of clients in the sampled service site within the  $j$ -th first-stage sampling unit in  $i$ -th stratum according to the same local reports, 22 is the length of the field period in weeks,  $L_{ij}$  is the length of the window in days,  $N_{ij}$  is the number of new enrollees during the window, and  $n_{ij}$  is the number of clients who are recruited into the evaluation study

 All newly enrolled pregnant women in April of 2010 plus 20 percent of newly enrolled infants. All from the PC2010.

 It is not necessary to define clients here as new enrollments although that would be best if possible. Of course, it is important to use whatever was used for sampling.

 New enrollees here means pregnant women enrolling for the first time during the current pregnancy plus new infant enrollees whose mothers appear not to have been on WIC during the gestation of the infant.

during the window. Here it is important to note that  $n_{ij}$  counts those who give informed consent and not just those who pass the screening test of not having previously enrolled for WIC during the current pregnancy or the pregnancy leading to the birth of the infant being enrolled.

Although this formula appears complex, we hope that the weights will have low variation. Various simplifications will come into play in different situations. For a given sampled service site, if the entries on the PC2010 identify the service site (rather than a composite site), the service site will have been sampled at the first stage of selection and no second stage of service site selection will have been needed; in this case we will have  $\frac{C_{ij}}{D_{ij}} = 1$ . Even when the second stage of service site

selection is needed, as long as the enrollment figures provided for second-stage selection are highly accurate,  $\text{corr}(M_{ij}, C_{ij})$  should be large and therefore the ratio  $\frac{C_{ij}}{M_{ij}}$  should be close to 1. If the

PC2010 data or the local scouting data turn out to be inaccurate, weights will vary more. On average, we expect the weights to be on the order of 550. This is based on an assumption of two million new enrollees in a year, 78 percent coverage, and a recruited sample size for the core sample of 2804.

Of course, to the extent that there is bad information at any phase or that there is a shift in site operations that reduces the predictive value of past data, the weights will vary. This is a concern because highly variable weights reduce the precision of survey estimates, and there is the potential for the cases with large outlying weights to have undue influence on estimates. Note that these weights will be constant within service site but vary across service sites. If there are isolated incidences of sites with weights much larger than the predicted average of 550, we will consider trimming the weights to avoid the situation where the results from such an office dominate the national estimates on a weighted basis. We are hopeful that this will not be required, but will carefully check for the possibility and take appropriate steps if the condition is detected.

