## 4.6 Recruit WIC Participants

[figure not shown]
Over a 5 month period beginning in January 2013 Westat will screen about 98 new WIC enrollees at each of 80 selected WIC service sites during a pre-determined enrollment period. The new enrollees will include prenatal mothers and postnatal infants <2.5 months old (whose mothers were not enrolled prenatally) who are enrolled at the service site or at outreach locations (hospital, mall, satellite sites) by staff in the service site. We expect to recruit about 55.4 new enrollees per site. The 80 WIC sites will be of varying sizes and therefore have vastly different enrollment flows (from 1.5 new enrollees per day up to 14 or more new enrollees per day). To accommodate the differences in enrollment flow the recruitment window at each site will range from 7 to 66 days (about 1 to 13 weeks). The enrollment start dates will be staggered and slightly frontloaded to ensure the sites with longer windows begin enrollment early in the period. Details of the sampling process can be found in the Final Sampling Plan in Deliverable 8b, submitted to FNS on February 17, 2012. Following is a description of our process for recruiting and training Westat staff, and a discussion of the steps in recruiting new WIC enrollees into the ITFPS-2.

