### Total Sample

When analyses use both the core and supplemental samples, a different set of baseweights will be required. Let  $r_{ijk}$  be the retention rate in the supplemental sample for persons in the sampling domain that contains the infant. The baseweight for the infant in the total sample will be

$W_{BTijk} = \frac{1}{1+r_{ijk}} W_{Bijk}$ . This same formula will be used whether the infant was sampled as part of the

core or as part of the supplemental sample. Note that if the infant is from a rare group that is always retained when found (such as children of black mothers), the weight for the infant in the total sample will be half the weight it receives when the core sample is analyzed by itself. At the other extreme, when an infant belongs to a common group that is never retained when found in the supplemental sample (such as children of obese Hispanic mothers), then the baseweight for the infant is the same whether the core is analyzed by itself or in combination with the supplemental sample.

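### As defined, the core base-weight formula does not give the stated average weight of about 550: it divides weeks by days, and its recruit count is not limited to the core sample

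*Combined protocol and SAP*

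**What the plan says.** Section 6.2 (Core Sample) gives the core weight as a product of six factors: 52/22 to annualise; M_i/(4M_ij) and E_i/2 for the two phases of site selection; C_ij/D_ij for the service site within a composite unit; a window factor; and N_ij/n_ij for enrollees seen over women recruited.

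The window factor is printed as 22L_ij/L_ij. Of its parts the text says that "22 is the length of the field period in weeks" and that L_ij "is the length of the window in days". Of n_ij it says that it "is the number of clients who are recruited into the evaluation study" during the window, and adds that only women who consent are counted. It does not mention core status.

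The same section then states: "On average, we expect the weights to be on the order of 550". It bases this on two million new enrollees a year, 78 percent coverage and "a recruited sample size for the core sample of 2804".

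The Total Sample part divides the core weight by 1 + r, where r is the retention rate of the woman's sampling domain in the supplemental sample. For a group that is always retained, the weight "will be half the weight it receives when the core sample is analyzed by itself".

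Section 4.6 adds "We expect to recruit about 55.4 new enrollees per site", at 80 sites, and "the recruitment window at each site will range from 7 to 66 days (about 1 to 13 weeks").

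**The concern.** A Horvitz-Thompson weight should be the inverse of the selection probability. The window factor should therefore be field period over window, both in the same unit. With 22 in weeks and L_ij in days, every weight is too small by the number of days counted in a week.

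The consequences differ by type of error.

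- **Scale.** A constant error leaves means, percentages and regression coefficients unchanged. Weighted totals, such as the Weighted n entries in the Appendix C shells, would be wrong. Section 6.3 rules out a final calibration to external totals, so no later step would restore the scale. Section 6.2 also judges outlying site weights against 550; if weights really average 111, a site at five times the average would look ordinary.
- **Relative weights.** Counting all recruits in n_ij lowers a site's weight as its share of retained supplemental women rises. Retention depends on subgroup, so the error follows each site's demographic mix and reaches means and percentages. The Total Sample rule would then deduct the supplemental women a second time.

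These base weights underlie every weight in Table 6-1 and are recomputed for each of the 40 replicates (Section 6.5).

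**Working it through.** **1. The plan's own figure.** From Section 6.2: 2,000,000 × 0.78 = 1,560,000 covered enrollees a year, and 1,560,000 / 2,804 = 556. The stated 550 reproduces.

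**2. Units.** If the window factor is field period over window, the first and fifth factors combine to (52/22) × (22/L_ij) = 52/L_ij. That is correct only if L_ij is in weeks.

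**3. Evaluating the formula.** Assumptions: 80 sites at two per stratum, so 40 equal strata; E_i = 4; C_ij/D_ij = 1; accurate size measures; constant enrollment flow. Let a be a site's annual enrollment and d the days counted per week.

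- Stratum size: 1,560,000 / 40 = 39,000, so M_i/(4M_ij) × E_i/2 = 39,000/(4a) × 2 = 19,500/a.
- Enrollees in the window: N_ij = a × L/(52d).
- Core recruits per site: 2,804 / 80 = 35.05. All recruits per site: 55.4 (Section 4.6).
- With core n_ij, W = (52/22) × (19,500/a) × window factor × [aL/(52d)] / 35.05 = 25.29 × (L/d) × window factor.

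| Window factor | n_ij core only | n_ij all recruits |
|---|---|---|
| 22d/L (one unit) | 556 | 352 |
| 22/L, d = 5 | 111 | 70 |
| 22/L, d = 7 | 79 | 50 |
| 22L/L, d = 5, L = 7 to 66 | 779 to 7,344 | 493 to 4,646 |
| 22L/L, d = 7, L = 7 to 66 | 556 to 5,246 | 352 to 3,319 |

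Only a common unit with core-only n_ij gives the stated value at every window length. With 22/L and core n_ij, the core weights sum to 1,560,000/5 = 312,000 or 1,560,000/7 = about 223,000, instead of 1.56 million.

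**4. The fraction as printed.** If 22L_ij/L_ij is the true text, the factor is 22 at every site and window length no longer adjusts the weight. Weights then spread 66/7 = 9.4-fold. To average 550 with core n_ij, the mean window would have to be 4.9 days (d = 5) or 6.9 days (d = 7), both below the 7-day minimum. With all recruits it would have to be 7.8 or 10.9 days, close to that minimum.

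**5. The recruit count.** 80 × 55.4 = 4,432 recruits, of whom 4,432 − 2,804 = 1,628 are not core. Literal n_ij gives 1,560,000 / 4,432 = 352, and the core weights sum to 2,804 × 352 = about 987,000, or 63% of 1.56 million. At a site with s retained supplemental recruits per core recruit, the weight is 556/(1 + s). The average s implied by the planned numbers is 1,628 / 2,804 = 0.58. Over an assumed range, s = 0.3 gives 428 and s = 0.9 gives 293.

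**6. Which day is meant.** Section 4.6 does not settle it. 66 days is 66/5 = 13.2 five-day weeks but 66/7 = 9.4 calendar weeks, so the upper end fits recruiting days. 7 days is 1.4 five-day weeks but exactly one calendar week. Enrollment days also vary by site: Section 4.2 plans to collect them, and its example clinic certifies on three days a week. At a three-day site, 22 weeks hold 66 recruiting days, so a fixed 110/L_ij would overstate its weight by 110/66 = 1.67, or 67%.

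**The case against.** The strongest reply is that this is notation. The 550 is correct on its own basis and is not derived from the formula. The printed numerator makes little sense and may be misread; a days-per-week conversion could have stood there. The cancelling fraction and the unit clash are also alternative readings, not two errors in one formula. The Core Sample heading, the 2,804 core recruits and the 1 + r rule all point to a core-only n_ij. A constant scale error does not touch the percentages, means and models that make up most of Table 7-2. The separate Sampling Plan, which was not available, may hold the operative formula.

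Much of this stands. The fraction should be checked against the source file, and core-only was probably the intention. The two readings are indeed alternatives, but neither gives 550. The section explains the purpose of the other constants and mentions no conversion, so an unseen one cannot be assumed. Context can guide a careful programmer on n_ij, but the sentence that clarifies the count addresses consent and leaves out core status. The limited effect on means applies only to a constant error. It does not cover literal n_ij or, if L_ij counts recruiting days, sites with different numbers of enrollment days per week.

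**Conclusion.** The concern holds. The expected average of about 550 is right; the formula and definitions meant to produce it are not. With the stated units and core-only n_ij the average is about 111 (recruiting days, five a week) or 79 (calendar days), too small by a factor of 5 or 7. With units fixed but n_ij read literally it is 352, and the shortfall varies by site. If the printed fraction is genuine, core weights run from about 780 to 7,300 on a five-day basis.

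The 5- and 7-fold factors follow from the stated units alone. The site-level figures rest on equal strata, E_i = 4, C_ij/D_ij = 1, accurate size measures and constant flow; the values 428 and 293 rest on an assumed range. This should be fixed before weights are programmed.

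**What to change.** - Write the window factor as field-period length over window length in one unit: both in weeks, both in calendar days, or the site's own recruiting days in the 22 weeks over its recruiting days in the window. State which kind of day L_ij counts. Do not use a fixed 110 unless every site recruits five days a week.
- Define n_ij as women assigned to the core sample who consent during the window. Keep N_ij as all new enrollees, so that N_ij/n_ij carries the core assignment.
- Check the printed fraction against the source file and make it agree with the definitions.
- Add a check, before any trimming, that core base weights average about 550 and sum to about 1.56 million.

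The cost is a correction to one formula and two definitions, plus one check. Section 4.2 already plans to collect each site's enrollment days, so no new data are needed.

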recruitment process of the sites. The recruitment of State agency directors will begin with a communication containing an advance letter, study fact sheet, answers to anticipated questions, and an invitation to participate in a 1-hour webinar (30-40 minutes for the presentation followed by a Q&A session of about 30 minutes). A follow-up letter will list the sampled sites under each State and will inform directors that they can invite key staff from the sampled local agencies and service sites to the webinar. The webinar will be recorded and be made available to those who could not attend the live session. During the webinar, Altarum will elaborate on information provided earlier and answer questions from those who participate. State agencies will be invited to be partners in the ITFPS-2 and State directors will be asked to assist with gaining the cooperation of their sampled sites. Approximately a week after the webinar, Altarum will begin to work with the States to finalize site participation details and to begin to compile a Local Site Profile Form for each site. The profile will include information such as hours of operation, percent of Spanish speaking participants and other information available from the State agency or local site. Altarum will summarize these details in a written communication with copies provided to the State agency, local site, and FNS. If a site requests, Altarum will prepare a memorandum of understanding (MOU).

In order to be chosen to participate in the ITFPS-2, a service site will need to identify all eligible WIC enrollees every day of the enrollment window. An eligible WIC enrollee is an English or Spanish speaking woman who is (1) pregnant and is enrolling in the WIC program for the first time for the current pregnancy; or (2) was not enrolled prenatally but is enrolling her infant who is less than 2.5 months old. We will consider sampled sites that cannot commit to identifying eligible women to be non-responders to the ITFPS-2.

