### 4.6.3 Recruitment and Enrollment Steps

Participant enrollment at the service site is presented in Figure 4.5, and described below.

1. **Identify Eligible WIC Enrollees.** WIC staff will identify all pregnant women in the designated study enrollment window who are enrolling in WIC for the first time for their current pregnancy and all infants less than 2.5 months whose mothers did not enroll prenatally. They will complete a 2-ply referral form that includes WIC ID, name, contact information, pregnancy status, age, and language. One copy will go to the woman (yellow); the other will be saved for the Westat recruiter/helper who will collect the forms at the end of the day.
2. **Intercept on site.** The Westat recruiter/helper will look for women holding a yellow referral form and attempt to intercept her at the end of her WIC visit in order to introduce the study and screen the woman. Barring that, they will make sure the woman gets a study flyer with a toll-free number she can call to learn more about the study. Barring that, they will make sure the woman gets a study flyer with a toll-free number she can call to learn more about the study.
3. **Introduce Study.** A Westat recruiter/helper will take the woman to a private space (designated for the ITFPS-2 recruitment activity by the site) and introduce the study. This will involve providing the woman with a study flyer that explains what participation in the study entails, the incentives, and how the mother can play an important role in understanding the health of all infants by joining the study. If a woman expresses interest in participating in the study but does not have time to go through the recruitment process, the recruiter/helper will obtain contact information and a Westat telephone recruiter will contact her to introduce the study and determine whether she is eligible.
4. **Assign to Core or Supplemental Sample.** The screener instrument will be programmed to assign participants to either the core or supplemental group in an alternating pattern. For sampling purposes it is necessary to assign a woman to one of these groups before we screen her. (See Sampling Plan, Deliverable 8 for details). In sites that have a Westat field recruiter, the recruiter will assign interested new enrollees to the core or supplemental sample using a laptop; in sites where a Westat helper has

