introduced the study, the helper will call a Westat number to make contact with a Westat telephone recruiter who will assign the woman to the appropriate sample.

5. **Administer Screener.** Westat recruiters (in-person or telephone) will administer the recruitment screener. In sites where the helper calls into the Westat telephone center to connect with a telephone recruiter, we will minimize wait time by monitoring call volume hourly during peak enrollment periods to ensure that all calls are picked up and linked with an interviewer immediately. When needed, we will be prepared to make adjustments to both the number of available toll-free staff and responsible interviewers.

The recruiter will confirm that the woman is eligible (i.e., has not been previously enrolled in WIC for her current pregnancy or that the infant is less than 2.5 months). Eligible respondents will be asked about their race, ethnicity, trimester of enrollment, pre-pregnancy BMI, household composition, and income. Core group participants will be retained irrespective of their responses to these questions. Participants assigned to the supplemental group may be found ineligible at this stage depending on their responses. Only rare population subdomains such as black mothers and infant who have no prenatal WIC exposure will be eligible for the supplemental group. Participants still eligible will also be asked questions to determine whether they plan to stay in the area during the study period, whether they are or will be the caregiver of the WIC infant, and their age. In addition, the interviewer will explain what participation involves; the number and types of interviews to be completed; and the incentive structure.

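### Footnote 12 defines the base-weight count N_ij without the study's age and language limits, so as written each site's weights are inflated by any ineligible share in that count

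*Combined protocol and SAP*

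**What the plan says.** Section 6.2 (Core Sample) gives the base weight as a product of factors, the last of which is N_ij/n_ij for site j in stratum i (N and n below).

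- **Numerator.** N is the number of new enrollees in the site's window. Footnote 12 defines the term for this purpose: "New enrollees here means pregnant women enrolling for the first time during the current pregnancy plus new infant enrollees". The infants meant are "new infant enrollees whose mothers appear not to have been on WIC during the gestation of the infant". No age limit and no language limit is stated.
- **Denominator.** n "counts those who give informed consent and not just those who pass the screening test", so it holds only women who were found eligible and then consented.
- **Eligibility.** Section 4.2: "An eligible WIC enrollee is an English or Spanish speaking woman who is" either pregnant and enrolling for the first time in that pregnancy, or who "was not enrolled prenatally but is enrolling her infant who is less than 2.5 months old".
- **Further screening.** Section 4.6.3, step 5, also asks "whether they plan to stay in the area during the study period, whether they are or will be the caregiver of the WIC infant", and the woman's age.
- **Data at hand.** In Section 4.6.3, step 1, WIC staff identify newly enrolling pregnant women and infants under 2.5 months without prenatal enrollment. "They will complete a 2-ply referral form that includes WIC ID, name, contact information, pregnancy status, age, and language".

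Section 6.2 also says that the weights are the same for everyone in a site and differ between sites. Section 6.3 rules out calibration to outside totals.

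**The concern.** A base weight is meant to be the inverse of a selection probability, which is the standard Section 6.2 sets for itself. An infant enrolled at four months, or a woman who speaks neither English nor Spanish, has no chance of selection. If such people are counted in N, the eligible recruits at that site are weighted up to represent them.

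Little in the later steps would undo this. The nonresponse adjustment in Section 6.3 redistributes existing base weight and so carries the inflation forward. The combined-sample weight is the core weight multiplied by 1/(1 + r), so it inherits the factor. The replicate weights repeat the same procedure. Trimming is considered only for isolated sites far above the expected average of 550. Calibration is not available.

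At stake are the weighted totals, which appear as a weighted n in the Appendix C table shells. Under a further condition, set out in the working, the national means and percentages are also affected.

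**Working it through.** **1. The plan's own figure.** Section 6.2 expects an average core weight of about 550, from two million new enrollees a year, 78 percent coverage and 2804 core recruits:

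2,000,000 × 0.78 / 2804 = 556.3.

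This reproduces the stated figure. The implied sum of weights is 2,000,000 × 0.78 = 1.56 million. The plan does not say what the 78 percent leaves out.

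**2. The inflation factor.** Let u be the share of N at a site that does not meet the eligibility rule, and N_e the eligible count. Then N = N_e/(1 − u), and

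N/n = (N_e/n) × 1/(1 − u).

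The other factors in the weight do not involve N, so the whole weight is multiplied by 1/(1 − u).

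**3. Effect on totals.** The documents give no value of u. The values below are assumptions, applied equally to all sites, and they take 556.3 as the correct average for eligible enrollees.

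| Assumed u | Factor 1/(1 − u) | Average weight | Sum of weights |
|---|---|---|---|
| 0 | 1.000 | 556 | 1.56 million |
| 2% | 1.020 | 568 | 1.59 million |
| 5% | 1.053 | 586 | 1.64 million |
| 10% | 1.111 | 618 | 1.73 million |
| 20% | 1.250 | 695 | 1.95 million |

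**4. Effect on percentages.** With site groups g holding true population shares s_g, outcomes p_g and factors f_g = 1/(1 − u_g), the estimate is Σ s_g f_g p_g / Σ s_g f_g. If every f_g is equal, it cancels and there is no bias. Bias needs u to vary between sites and to be related to the outcome. Two illustrations, all inputs assumed:

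- *Some sites affected, the rest with u = 0.* With 10% of the population in affected sites, u = 10% and an outcome gap of 10 points, the affected share becomes 0.1111/1.0111 = 0.1099. The percentage moves by 0.0099 × 10 = 0.1 point and the total rises by 1.1%. With 20% affected, u = 20% and a gap of 20 points, the share becomes 0.25/1.05 = 0.2381. The percentage moves by 0.0381 × 20 = 0.8 points and the total rises by 5%.
- *Two equal groups of sites, outcomes 60% and 80%, true mean 70%, with the larger u in the second group.* Shares of 2% and 10% give 70.4%; 5% and 20% give 70.9%; 5% and 30% give 71.5%. Shares of 5% and 5% give exactly 70%.

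**5. Effect on precision.** In the two-group illustration the added design effect from unequal weights is at most 1.02, so variance is not the issue.

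**The case against.** The strongest reply is that footnote 12 is shorthand. Section 4.6 describes the new enrollees screened in the window as prenatal mothers and infants under 2.5 months, so the term already carries the age limit elsewhere. Section 6.2 abbreviates the screening test for n in the same way, omitting age and language there too. The only person-level identification of window enrollees that the plan describes is restricted: Section 4.2 requires sites to identify eligible enrollees, and the staff step in Section 4.6.3 covers only infants under 2.5 months. Nothing describes a count of older infants. The Sampling Plan, to which Sections 4.6 and 4.6.3 refer for details, may settle how N is counted.

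Much of this stands. If N is tallied from the referral forms, the older-infant part of the problem disappears. A reader might infer from footnote 12 that older infants will in fact be counted, or that national percentages will be biased by amounts that differ by site. The documents support neither: they give no ineligible share for any site, and no evidence that the share varies or is related to feeding outcomes.

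Three things are left. Footnote 12 is worded as a definition for the weighting, and Section 6.2 names no data source that would override it. The staff step refers to all newly enrolling pregnant women, and the form records language, so other-language women may be on the forms; nothing says that they are removed from N. The questions in step 5 may exclude further women, and nothing says how they or the unscreened enrollees are treated. The Sampling Plan is not part of these documents and cannot be assumed to close the gap.

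**Conclusion.** The concern holds as a defect of definition, of unknown size. As written, N covers a wider population than n, and a site with ineligible share u has its base weights multiplied by 1/(1 − u): 1.11 at an assumed 10%, 1.25 at an assumed 20%. Weighted totals are too high whenever u exceeds zero. Means and percentages are affected only if u varies between sites and is related to the outcome; under the assumed inputs above the shift runs from 0.1 to 1.5 points, and it is zero if u is uniform. If N is counted from the referral forms, only the language part and any exclusions at the step 5 screener remain. The defect deserves correction because it sits in the base weight from which the other weights are built and no calibration step would correct it.

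**What to change.** Rewrite footnote 12 so that N is the number of enrollees in the window who meet the Section 4.2 rule, and name the source:

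1. Count N from the referral forms, which already cover only infants under 2.5 months.
2. Remove women who speak neither English nor Spanish, using the language recorded on the form.
3. Remove enrollees found ineligible at the core screener (Section 4.6.3, step 5), and state which answers there make a woman ineligible.
4. Multiply the count of unscreened enrollees by the eligibility rate observed among those screened at the site, or a pooled rate where the site's numbers are small.

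Women assigned to the supplemental sample and not retained because of their subgroup are not ineligible in this sense. The retention rate in the Total Sample weight already handles them, so they should stay in N.

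The cost is one footnote and a short tallying rule. The forms and screener results are already to be collected. The rule should be settled before the site windows open, because form counts are easier to secure at enrollment than to reconstruct later.
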